Study subjects will be recruited through referral for surgical consultation in the neurosurgery outpatient clinic at Mayo Clinic Rochester. Individual surgeons will determine whether a surgery is indicated in particular patients. After the decision has been made to proceed with surgery, the patient will be interviewed for eligibility into the study, consented, and enrolled by the respective neurosurgeon's physician extender (R.N. or N.P.). Eligibility criteria are included in Table 1 and will be reviewed with each patient during the preoperative visit addressing the eligibility requirements for entry into the study. Patients undergoing simple spinal procedures (discectomy and foraminotomy procedures) that typically have next day hospital discharges and low incidences of POUR will be excluded from the study. It is not anticipated that subject retention will present a major challenge because the duration of study follow up is limited to the duration of the postoperative hospital stay. It is estimated that subjects will be actively participating in the study for approximately 8-12 days in most cases. Subject recruitment will continue until at least 175 subjects have been recruited into both the treatment and control groups and have completed the study. An interim analysis will be performed with unblinded data from the research pharmacy when 75 or more patients have completed participation.

Inclusion Criteria	Exclusion Criteria
≥ 35 years (Males & Females)	< 35 years
Cervical Laminectomy Cervical Posterior Fusion Cervical Anterior/Posterior Fusion	Cervical Anterior Discectomy and Fusion Cervical Anterior Corpectomy Cervical Posterior Discectomy Cervical Foraminotomy
Lumbar Laminectomy Lumbar Posterolateral Fusion Lumbar Interbody Fusion	Lumbar Discectomy (METRx or Open) Lumbar Foraminotomy Lumbar Anterior Fusion
	Myelopathy with bladder dysfunction
	Patients currently taking an alpha- antagonist [#]
	Patients with history of allergy or sensitivity to tamsulosin or other alpha-antagonist
	History of prostatectomy or urologic surgery involving the bladder or urethra
	Severe liver disease or end-stage renal disease

Table 1:

	Patients taking strong inhibitors of CYP3A4*
	Mental disability or prisoner

[#]The following drugs are alpha antagonists: alfuzosin, doxazosin, prazosin, terazosin, tamsulosin, and phenoxybenzamine.^{46,47}

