Pre-operative Post Void Residual Urine Volume:

A pre-operative post void residual (PVR) volume of urine will be obtained on all enrolled patients at their pre-operative clinic visit prior to beginning their drug assignment (tamsulosin or placebo). This will be measured using the same technique as will be performed during the post-operative period (see Outcome Measures below). This baseline PVR will help determine efficacy of the study drug as outcomes are measured. The residual will be done by a member of the study staff and patients will not be charged.

Outcome Measures:

The primary outcome measure will be the incidence of POUR. POUR will be defined as any of the following:

- 1) Estimated post-void residual (PVR) volume of urine greater than or equal to 300 mL.
- 2) Estimated retention urine volume of greater than or equal to 500 mL in patients unable to void.
- 3) Patients experiencing discomfort or distension and unable to void with lesser residual urine volume than 500 ml

Neurosurgical nursing staff currently follow the institutional Urinary Retention Protocol (MC1156-214rev0610.) This protocol includes an algorithm for both diagnosing postoperative urinary retention and its treatment. This protocol has been in use for all postoperative spine patients since 2003 and the most current version is based on the above definition of urinary retention. All residual volume of urine measurements will be made with a standard bladder scanner instrument that is currently in use on the neurosurgery wards. Presence or absence of urinary retention will be recorded in the electronic medical record (EMR) for later data retrieval and analysis.

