Secondary outcome variables include duration of POUR among those patients in which it occurs, number of intermittent catheterizations in those with urinary retention, incidence of UTI, and duration of hospital stay. Measurement of the duration of POUR will closely coincide with the methods for recording incidence of POUR as discussed above. The decision to use and the time of removal of indwelling urinary catheters will be left to the discretion of the primary neurosurgical team. Time of indwelling catheter removal after surgery will serve as time zero for beginning calculation of postoperative urinary retention duration if the patient later requires in and out straight catheterization. For patients without an indwelling catheter, the time patients leave the operating room will serve as time zero. Per the Urinary Retention Protocol (MC1156-214rev0610),

patients found to be experiencing POUR will be ordered to have a straight in and out catheterization performed by a member of the catheterization team after failure of noninvasive measures (e.g. trigger techniques, bladder massage, application of warmth, relaxed environment, privacy, ambulation) by the attending nursing staff member. Urinary retention will be considered resolved after two consecutive post-void residual urine scans have demonstrated less than 300 ml residual urine volume in a patient spontaneously voiding. The number of intermittent catheterizations is recorded in the EMR in accordance with the standardized protocol.

Patients suspicious of having a UTI based on signs and symptoms of urinary frequency, urgency, burning or pain will have a urine sample (via catheterization or spontaneous void) sent for routine urinalysis, gram stain, and culture/sensitivity by the nursing staff member responsible for the patient or the primary neurosurgical team, per instructions documented on the Urinary Retention Protocol (MC1156-214rev0610). Positive UTIs will be defined as positive gram stain in the presence of signs or symptoms of UTI, urine white blood cell count elevation, and positive culture of >10⁴ cfu/ml. Patients will be treated with the appropriate antibiotic based on culture sensitivity.

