Length of hospital stay will be recorded for all patients following the surgical procedure with the day after surgery defined as postoperative day one. The medical record will be reviewed following discharge to determine if hospital discharge date was dependent on POUR or other reason (e.g. uncontrollable pain, mobility requiring physical therapy or inpatient rehabilitation, or other medical complications delaying discharge).

In addition to the primary and secondary outcome measures, baseline characteristics will be collected on all patients via the medical record including age, height and weight, past history of postoperative urinary retention or diagnosis of benign prostatic hyperplasia (not on treatment), length and type of surgery, estimated blood loss during surgery, total intravenous fluids administered perioperatively, time to oral analgesic use (in hours), total analgesic use during the postoperative period, time to first postoperative mobility (in hours), and any adverse events thought to be related to administration of the study medication. These variables will be used as baseline comparisons between the two groups to ensure homogeny and be used in statistical adjustment if differences between the groups are significant after randomization.

Unanticipated events:

There is the potential for patients to experience urinary retention as outpatients after inpatient urinary retention has resolved. This is quite unusual to occur after urinary retention has resolved as defined above and may indicate the patient needs further investigation by a urologic surgeon. Patients will be counseled by nursing staff prior to dismissal regarding the signs and symptoms of urinary retention and directed to seek medical attention with appropriate urology referral should the treating physician deem this is appropriate.

Patients experiencing prolonged postoperative urinary retention (> 5 days) will be seen by the urology consult service for recommendations regarding further investigation and treatment. The study group designation may be broken at this point to determine which group the patient is in regarding treatment medication if deemed necessary by the urology consult service to guide further treatment.

Patients experiencing severe adverse events such as profound hypotension, arrhythmia, or allergic reaction will be evaluated by the primary neurosurgical team with appropriate intervention or consultation as deemed necessary.

Quality Control:

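### Retention already present before the first dose can count as incident POUR, and no rule uses the baseline PVR that is measured in every patient

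*Combined protocol and SAP*

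**What the plan says.** All places are in the combined protocol and SAP.

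- **Pre-operative Post Void Residual Urine Volume.** The scan is done in everyone before the assigned drug is started: "A pre-operative post void residual (PVR) volume of urine will be obtained on all enrolled patients". It is comparable with the later scans: "This will be measured using the same technique as will be performed during the post-operative period". Its purpose is put in general terms: "This baseline PVR will help determine efficacy of the study drug as outcomes are measured".
- **Outcome Measures, POUR criterion 1.** "Estimated post-void residual (PVR) volume of urine greater than or equal to 300 mL". The criterion makes no reference to the baseline value.
- **Table 1 (Subject Recruitment and Retention).** There is no PVR limit. The nearest exclusions are "Myelopathy with bladder dysfunction" and "History of prostatectomy or urologic surgery involving the bladder or urethra"; current users of an alpha-antagonist are also excluded.
- **Outcome Measures, baseline characteristics.** The list includes "past history of postoperative urinary retention or diagnosis of benign prostatic hyperplasia (not on treatment", so such patients may enter. Baseline PVR is not on this list, which also supplies the variables for any later adjustment.
- **Analysis of the Data.** The primary test is an unadjusted chi-squared or Fisher's exact test, with intention to treat for every comparison. Adjustment is considered only if the groups turn out to differ at baseline.
- **Outcome Measures, resolution.** "Urinary retention will be considered resolved after two consecutive post-void residual urine scans have demonstrated less than 300 ml residual urine volume".

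**The concern.** Hypothesis 1 is about the incidence of retention after surgery. A patient with a PVR of 350 mL before the first dose and 350 mL after surgery has no new retention, yet meets criterion 1. The trial can identify this patient from a scan it already performs, but nothing in the endpoint or the analysis does so.

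Two things are at stake. First, the reported rate would mix existing with new retention. Second, events that occur in both arms regardless of the drug narrow the difference and raise the variance, which costs power. There is also a smaller issue. The plan says the baseline PVR will inform efficacy but gives no rule, so its use could be chosen after the results are known.

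**Working it through.** **Inputs from Analysis of the Data.** Control rate 0.20, tamsulosin rate 0.10, one-sided alpha 0.05, power 0.80, 175 per arm (219 if two-sided). The share *f* of patients with baseline PVR of 300 mL or more is not in the documents. I assume 1, 2, 5 and 10%.

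**The plan's own figure.** With mean rate 0.15 and d = 0.10:

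n = [1.645 × √(2 × 0.15 × 0.85) + 0.842 × √(0.09 + 0.16)]² / 0.10² = 156.6, or 157 per arm.

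With the continuity correction, n′ = (n/4) × [1 + √(1 + 4/(n d))]² = 176.04, or 177 per arm. The two-sided versions are 199 and 219. The plan's 175 and 219 therefore match the continuity-corrected formula, the first to within two patients and the second exactly.

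**Power of the planned test.** I add the binomial probabilities of all pairs of event counts for which the one-sided Pearson statistic reaches 1.645. At 0.20 against 0.10 with 175 per arm this gives 0.843. On the continuity-corrected basis it is 0.798.

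**Scenario 1: no drug effect in these patients, and all of them are events.** The 20% and 10% hold among the rest, so the rates become f + (1 − f) × 0.20 and f + (1 − f) × 0.10.

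| f | Control | Tamsulosin | Exact power | Continuity-corrected power |
|---|---|---|---|---|
| 0 | 20.0% | 10.0% | 0.843 | 0.798 |
| 1% | 20.8% | 10.9% | 0.820 | 0.774 |
| 2% | 21.6% | 11.8% | 0.798 | 0.750 |
| 5% | 24.0% | 14.5% | 0.733 | 0.683 |
| 10% | 28.0% | 19.0% | 0.638 | 0.585 |

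**Changing one premise at a time** (exact power, unadjusted test, 175 per arm):

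| Premise | f = 2% | f = 5% | f = 10% |
|---|---|---|---|
| Only half are events after surgery, no drug effect in them | 0.816 | 0.774 | 0.703 |
| Drug lowers retention in them by 20% | 0.829 | 0.814 | 0.800 |
| Drug lowers retention in them by 25% | 0.836 | 0.831 | 0.833 |
| Drug halves retention in them | 0.871 | 0.905 | 0.947 |
| Planned 20% already includes them; drug halves new cases only | 0.758 | 0.604 | 0.339 |

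For example, at f = 5% and a 25% reduction the tamsulosin rate is 0.05 × 0.75 + 0.95 × 0.10 = 13.25%, against 24.0% on control. A 25% reduction is about break-even: power is within 0.007 to 0.012 of 0.843. The last row loses more than Scenario 1 because it also shrinks the number of preventable events. It depends on reading the planning rate as including existing retention, which the documents do not settle.

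**Remedies compared** (175 randomised per arm, 20% against 10% among the rest):

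| Analysis | f = 2% | f = 5% | f = 10% |
|---|---|---|---|
| Unadjusted, no effect in these patients | 0.798 | 0.733 | 0.638 |
| Restricted to baseline below 300 mL (172, 166, 158 per arm) | 0.837 | 0.829 | 0.811 |
| Stratified, no effect in these patients (simulated) | 0.836 | 0.825 | 0.804 |
| Stratified, drug halves retention in them (simulated) | 0.881 | 0.932 | 0.976 |

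A stratum in which everyone is an event adds nothing to the numerator or the variance of a stratified test, so the lost power comes back. If the drug does work in that stratum, its contribution is kept. Restriction would discard it.

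**The case against.** A reader might infer that the primary comparison is diluted as a matter of fact. The documents do not support that; it needs three premises.

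- **Prevalence.** None is given, and the exclusions for bladder dysfunction with myelopathy, prior urologic surgery and current alpha-antagonist use remove likely sources. At 1% the exact loss is only 0.843 − 0.820 = 0.023.
- **Persistence.** POUR is assessed after surgery, following five days of study drug and a dose on the morning of surgery. A high baseline value does not itself meet the endpoint.
- **No drug effect.** This is the weakest premise. The Background says that tamsulosin relieves bladder outlet obstruction and cites efficacy against retention and voiding difficulty in women. Untreated prostatic hyperplasia, one possible source of high baseline values, is its approved indication. If the drug halves retention in these patients, power rises.

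All three objections stand, and they turn a certain loss into a possible one. It is also fair that making a restricted set the primary analysis would depart from the stated intention-to-treat rule and might drop patients in whom the drug works.

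What they do not answer is the gap itself. The endpoint does not separate new from existing retention, and the use promised for baseline PVR has no rule. A gain from relieving existing retention would also not be prevention of postoperative retention, which is a reason to show these patients separately.

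**Conclusion.** The point holds as a gap in specification with a conditional cost. The endpoint can count existing retention as incident, and nothing in eligibility or analysis uses the baseline scan that would show it.

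Randomisation balances baseline PVR in expectation, so a reader who infers bias between arms goes too far. The possible loss runs from 0.023 of power at an assumed 1% to 0.205 at 10% (0.843 − 0.638). This holds if 20% against 10% applies to all other patients, every high-baseline patient is an event and the drug does nothing in them. It essentially disappears at about a 25% reduction in these patients and reverses beyond that. It is larger if the planned 20% already includes them.

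A reader might also infer that baseline retention leaves POUR durations without an end. The resolution rule can go unmet in any patient discharged while still retaining urine. That is a general censoring gap, not one created by baseline PVR.

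**What to change.** In Analysis of the Data:

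1. Keep all randomised patients in the primary intention-to-treat analysis. Replace the unadjusted test with one stratified on pre-treatment PVR (below 300 mL against 300 mL or more), for example Cochran-Mantel-Haenszel, or with an analysis of the binary outcome adjusted for baseline PVR.
2. Prespecify, as a sensitivity analysis for both incidence and duration of POUR, the comparison restricted to baseline PVR below 300 mL. The scan precedes the first dose, so this subset keeps the randomised comparison.
3. Add baseline PVR to the listed baseline characteristics, and report the share at 300 mL or more, so that readers can judge which scenario applies.

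The scan is already planned, so the cost is wording and slightly more analysis work. Eligibility, sample size and patient care do not change.

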*The following drugs are strong inhibitors of CYP3A4: ketoconazole, itraconazole, clarithromycin, ritonavir, indinavir/ritonavir, lopinavir/ritonavir, and conivaptan.⁴⁸

Randomization:

A consecutive sample of subjects that meet eligibility requirements and give informed consent will be randomized to two study groups via a randomization number generated from a random numbers table. Based on their randomization number patients will be given a prescription (for either tamsulosin or a likeappearing placebo) from the Mayo pharmacy at least one week prior to the date of surgery. The pharmacy will record which group the patient has been assigned to in a central pharmacy database. This database will then be used in the perioperative and postoperative period to maintain the patient's drug designation and administration while in the hospital. The randomization will be blinded to both the treating physician's team and the patient until the end of the study and data analysis is undertaken.

Drug Administration:

In order to achieve full steady state concentrations of the drug by the time of surgery, patients will be instructed to take the assigned drug for 5 days prior to surgery, as well as the morning of surgery. Thus, patients will be given 6 pills of the study medication or the like-appearing placebo at a preoperative clinic visit. On the morning of surgery patients will be admitted to Saint Marys Hospital as morning admissions and proceed to surgery that day based on the surgical schedule. Data on medication compliance will be collected and recorded at that time. Patients will continue taking tamsulosin 0.4mg or like-appearing placebo provided by the Mayo Pharmacy beginning on post-operative day one and continuing every day during their postoperative hospital course until the time of discharge. At that time the primary treating team will write an order to discontinue the study medication. Because each patient will be at therapeutic steady state concentrations of the drug by the time of surgery, shorter hospital stays should not underestimate the potential treatment benefit of this medication. Standard postoperative orders for patients undergoing decompressive cervical or lumbar laminectomy and/or spinal fusion have been in place for neurosurgical patients and will continue to be used during this study (postoperative order set

MC1156-404). The cost of the study medication will be covered by the study and patients will not be charged.

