All statistical analysis and report of results will be done in a confidential manner and no information linking individual patients with data from the study will be shared outside of the study. Every effort will be made to keep this data anonymous once it has been collected.

Analysis of the Data:

Baseline characteristics will be compared between the two study groups using a chi-squared or Fisher's Exact Test for categorical variables and multiple two sample t-tests for continuous variables. The primary outcome variable, incidence of POUR, as well as other categorical variables, such as incidence of UTI, will be analyzed using a chi-squared test or Fisher's Exact Test. Duration of POUR will be compared using a two sample non-paired t-test comparing means. An appropriate nonparametric test (e.g. Wilcoxon Rank Sum) will be used for non-normal appearing data as can be anticipated for length of hospital stay. Differences in the groups with respect to baseline variables will be used to construct a multiple linear regression model to control for potential confounding factors if necessary. Intention to treat analysis will be used for all comparisons between groups.

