The primary outcome measure of incidence of POUR was used to calculate sample size. Data gathered from multiple series suggests that postoperative urinary retention occurs in 2-69% of patients undergoing a variety of surgical procedures, with 38% occurring in neurosurgical patients undergoing simple decompressive spinal procedures. Using 20% (P2=0.20) as a conservative estimate of incidence, an effect size of 10% for the primary outcome variable (P1=0.10) would be clinically meaningful. Thus, P2-P1 = 0.10. Because incidence of urinary retention is a binary categorical variable, a chi-squared test can be used to compare groups. Based on a type I error rate of 0.05 (α), a type II error rate of 0.20 (β), and power of 0.80 the estimated sample sizes needed for each group are as follows. For a one sided type 1 error, there would need to be 175 subjects in each group. For a two-sided type 1 error there would need to be 219 subjects in each group. A one-sided test of significance is reasonable in this study because an increase in incidence of POUR experienced in the tamsulosin treated group is not anticipated and would not add additional useful information in terms of using tamsulosin for POUR. Thus, a reasonable estimate for sample size is 175 subjects in both the treatment and control groups. Furthermore, with 175 patients per arm, there would be 87% power to detect a 1 day difference in the duration of urinary retention and duration of hospital stay with a 1-sided significance level of 0.05 (this assumes an effect size for this secondary outcome variable of 0.30 [1 day difference in means/pooled standard deviation estimate of 3.33]).

Role in Project:

[name]: Co-Principalinvestigator for the study, responsible for study design, study implementation, data collection, reporting of adverse events, and manuscript preparation.

[name]: Co-investigator responsible for assisting in study implementation, data collection, and manuscript preparation.

[name]: Co-investigator responsible for IRB application, Informed Consent form, and pharmacy liaison.

[name]: Statistician responsible for overseeing statistics performed by the co-PI as part of the CTSA BERD program.

[name]: Member of the Office of Research and Regulatory support who will be assisting with the Investigational New Drug application and corresponding with the FDA.

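### Variables that arise after study drug are treated as baseline and adjusted for when they differ, while pre-drug PVR has no named analysis and binary POUR has no suitable adjusted model

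*Combined protocol and SAP*

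**What the plan says.** Five places in the combined protocol and SAP bear on this.

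- **Pre-operative Post Void Residual Urine Volume.** PVR is taken on all enrolled patients at the preoperative clinic visit, before the first dose and by the same technique as after surgery. Its purpose is stated: "This baseline PVR will help determine efficacy of the study drug as outcomes are measured".
- **Drug Administration.** Study drug starts well before the operation: "patients will be instructed to take the assigned drug for 5 days prior to surgery, as well as the morning of surgery".
- **Outcome Measures, baseline characteristics.** The open-ended list mixes pre-drug items such as age with items such as "estimated blood loss during surgery, total intravenous fluids administered perioperatively, time to oral analgesic use (in hours), total analgesic use during the postoperative period". It also contains time to first mobility and adverse events thought to be related to study drug. PVR is not named. All of these serve as baseline comparisons and are to "be used in statistical adjustment if differences between the groups are significant after randomization".
- **Analysis of the Data, tests.** The primary comparison is unadjusted: "The primary outcome variable, incidence of POUR, as well as other categorical variables, such as incidence of UTI, will be analyzed using a chi-squared test". An exact test is the named alternative. Differences in baseline variables will be used to "construct a multiple linear regression model to control for potential confounding factors if necessary". No outcome is attached to that model, and neither section gives a threshold for adjusting.
- **Analysis of the Data, sample size.** "Because incidence of urinary retention is a binary categorical variable, a chi-squared test can be used to compare groups".

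**The concern.** An adjusted analysis of a randomised trial should use covariates that treatment cannot have changed, chosen before the data are seen. This rule departs from both requirements. Half of the listed characteristics arise after dosing has begun, and a covariate enters because the arms differ on it. For a variable measured after dosing, a difference between arms may itself be an effect of the drug. The rule is then most likely to select the variables that least belong in the model.

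Meanwhile, the one pre-drug measurement on the same scale as the first POUR criterion (postoperative PVR of at least 300 mL) is collected with a stated efficacy purpose but given no analysis. If an adjusted POUR result were wanted, the analyst would have to choose both the model and the covariates after seeing the data. What is at stake is the credibility of any adjusted estimate, and some precision. The primary test is not at stake.

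**Working it through.** **1. The plan's own figure.** Inputs from Analysis of the Data: 20% versus 10%, one-sided 0.05, power 0.80.

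n = [z₀.₉₅ √(2 × 0.15 × 0.85) + z₀.₈₀ √(0.10 × 0.90 + 0.20 × 0.80)]² / 0.10² = [1.645 × 0.505 + 0.842 × 0.500]² / 0.01 = 156.6, so 157 per arm.

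With continuity correction, (n/4)[1 + √(1 + 4/(n × 0.10))]² gives 177, close to the stated 175. The two-sided version gives 219, as stated. At 175 per arm, power is 83.8% uncorrected, since (√175 × 0.10 − 0.8306)/0.5 = 0.985, and 79.8% with the correction.

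**2. Sorting the list in Outcome Measures.**

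| Settled before study drug | Arising at or after surgery |
|---|---|
| age, height, weight, prior POUR, untreated BPH, type of surgery (as planned) | length of surgery, blood loss, intravenous fluids, time to oral analgesic, total analgesic use, time to mobility |

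That is 6 + 6 = 12 variables, with drug-related adverse events in addition. By Drug Administration, every item in the right-hand column follows five days of study drug.

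The protocol itself suggests how some could be affected. Adverse Events names orthostatic hypotension as the main risk, which could bear on fluids and mobility. Outcome Measures lists ambulation among the measures tried for retention, so mobility may also respond to the outcome. With such a variable in the model, the arm coefficient no longer estimates the drug's total effect on POUR. The documents give no estimate of these links, so the bias cannot be sized.

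**3. How often the trigger would use PVR.** PVR precedes dosing, so a test of group difference at level α fires by chance in about α of trials. Simulated rates were 4.6–5.5% at p<0.05, 9.5–10.2% at p<0.10 and 19.2–20.4% at p<0.20. All three thresholds are assumed, because the plan gives none. If the 12 listed variables were independent and unaffected by drug, at least one would trigger at 0.05 with probability 1 − 0.95¹² = 0.46. That is illustrative only, since the variables are surely correlated.

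**4. What a fixed model would change.** Simulation: 20,000 trials per setting, 175 per arm, 20% versus 10%, one-sided 0.05. The logistic model has arm, PVR, age, region and fusion (likelihood-ratio test); age, region and fusion are given no effect. PVR is assumed normal, with assumed odds ratios because the documents give none.

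| PVR odds ratio per SD | Unadjusted | Logistic | Gain (points) |
|---|---|---|---|
| 1 | 84.1% | 84.0% | −0.1 |
| 1.5 | 85.0% | 85.6% | 0.6 |
| 2 | 84.2% | 86.1% | 1.9 |
| 2.5 | 84.3% | 87.3% | 3.0 |
| 3 | 83.9% | 88.4% | 4.5 |

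Monte Carlo standard error is about 0.25 point. A separate simulation (8,000 trials, PVR-only logistic model, Wald test) gives gains of −0.1, 0.5, 1.5 and 3.8 points at odds ratios 1, 1.5, 2 and 3. With a lognormal PVR (log-SD 0.8), the five-term gains run from −0.1 to 6.5 points. Triggering at p<0.05 recovers only about half a point with a normal PVR.

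At 15% in both arms, size was 4.8–5.1% unadjusted and 5.0–5.3% for the logistic model.

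**5. Can the data carry the model?** Expected events are 175 × (0.20 + 0.10) = 52.5. Over five terms, that is 10.5 per term.

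**The case against.** The strongest reply has four parts.

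*The primary analysis is a valid unadjusted test.* This stands in full. A reader might infer from the adjustment rule that the primary result is biased. It is not: the chi-squared or Fisher comparison uses no covariates.

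*The post-surgical variables are recognised risk factors.* Background lists duration of surgery, perioperative fluids and postoperative analgesia as such, and length of surgery is unlikely to respond to tamsulosin. That justifies recording and describing them by arm. It does not justify adjusting for them as baseline, because being prognostic does not make a variable unaffected by treatment.

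*PVR has a generic route into the analysis.* It is called a baseline measure, and the list is open-ended. So it is too strong to say that PVR cannot be used at all. But the only routes are a comparison of the arms and adjustment conditional on imbalance, and neither delivers the efficacy role claimed for it.

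*The linear model may be meant for duration or length of stay.* It follows the sentences on those outcomes, where linear regression is ordinary. The text therefore does not show that linear regression is planned for POUR. Even if it were so used, simulation gave size of 4.8–5.1% and power of 84.4–87.0%, with negative fitted risks for 0.1% to 12% of patients as the odds ratio rises from 1 to 3. What survives is narrower: no adjusted model suited to a binary POUR outcome is specified.

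**Conclusion.** The concern holds as a fault in the adjustment rule. The rule as written admits variables arising after study drug, and even drug-related adverse events, as baseline covariates when they differ significantly. That can remove part of the drug effect and bias the adjusted estimate. The possibility follows from the timing alone; its size is unknown, and the documents show no actual drug effect on any of these variables.

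A reader might also infer that bringing in PVR would give this trial up to 4.5 more points of power. The documents do not support that. They give no PVR–POUR association, so the range rests on assumed odds ratios of 1 to 3 per SD and a normal PVR. The base is the uncorrected chi-squared test at about 84%, whereas the stated 175 is close to what the continuity-corrected calculation requires, with power of about 80%. The gain would exist only if the adjusted model were primary. As a supporting analysis it leaves primary power unchanged and offers a cleaner, perhaps somewhat more precise, adjusted estimate.

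Priority is low.

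**What to change.** Settle the following before any unblinding, including the unblinded interim analysis that Subject Recruitment and Retention plans once 75 or more patients have completed:

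1. Delete the rule that adjusts when group differences are significant.
2. Limit adjustment covariates to values fixed before study drug. Report the surgical and postoperative variables by arm as descriptive data, and adverse events as safety data.
3. Prespecify one logistic regression of POUR on arm, continuous pre-drug PVR, age and planned (not performed) surgery type. Fit it on the intention-to-treat set whatever the observed imbalance, at the same one-sided level as the primary test. Report an odds ratio and a standardised risk difference.
4. State how a missing PVR is handled, for example by imputing the pooled mean without reference to arm or outcome.
5. State whether this model is supporting, with chi-squared kept as primary, or is itself primary.
6. Say which outcomes the multiple linear regression is for.

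The cost is wording only. PVR, age and type of surgery are already collected; planned surgery type needs only to be recorded as known at enrolment.
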